10.6. Pharmacodynamics

Pharmacodynamic blood samples of approximately 10 mL will be collected in Parts A and B as specified in the Schedule of Events ([Appendix 2](#)).

Plasma TG, TC, and high-density lipoprotein cholesterol (HDL-c) (to calculate LDL-c and non-HDL-c) will be assessed in the fasted state for the first 4 hours postdose and then again during the post-prandial period following a high-fat meal administration at 4 hours postdose in Part B. Changes in these PD markers from baseline (Day -1) and Day 28 will be assessed at each dose level to find at least 1 dose level that shows evidence of target engagement by a decrease in fasting or post-prandial lipids.

The lipid lowering ability of LY3202328 in subjects with a statin-free background will be quantified by TG, TC, and HDL-c (to calculate LDL-c and non-HDL-c) in Parts A and B, and by LDL-c ultracentrifugation methods in Part B only.

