- e A full physical examination with neurological assessments will be performed (predose) on the scheduled days. Symptom-driven physical or neurological examination may be performed at other times, at the investigator's discretion.
- f Single 12-lead ECGs to be collected during Screening and on Day –2. Triplicate ECGs (spaced approximately 1 minute apart) to be collected on Day –1. The decision to collect triplicate or single ECGs at all remaining time points will be made based on ECG data from Part A (triplicate ECGs are planned). Subjects must be supine for at least 5 minutes prior to ECG collection. When ECG collections are scheduled at the same time point as any other tests, ECGs, followed by vital signs, must be recorded prior to any clinical laboratory, PK, PD, or biomarker blood sampling.
- g Vital signs to be measured include respiratory rate (Screening and Day –1, Hour –1 only) blood pressure, pulse rate, and temperature. Orthostatic blood pressure and pulse rate to be measured at all specified time points on from Day –1 to study discharge.
- h Refer to [Appendix 3](#) for the serum chemistry, hematology, and urinalysis clinical laboratory tests.
- i Samples for serum chemistry will be obtained following a fast of at least 8 hours or 12 hours when a fasting simple lipid assessment (i.e., TC, TG and HDL-c) is will be performed at the same time. In case of dropouts or rechecks, subjects may not have fasted for 8 hours or 12 hours, as applicable, before the serum chemistry sample is taken. Lipid panel will also be assessed during the post-prandial lunch period on Days –1 and 28.
- j Serum pregnancy tests to be performed on female subjects only; serum FSH tests to be performed on postmenopausal female subjects only.
- k Subjects will be discharged following Hour 24 procedures (i.e., Days –6 and 2).
- l Serum TC, TG, and HDL-c will be measured; HDL-c will be used to calculate LDL-c and non-HDL-c.
- m Collection to occur just prior to meal.
- n Collection to occur prior to the relative dosing time/prior to dosing.
- o Low-density lipoprotein cholesterol for PD analysis will be evaluated by ultracentrifuge.
- p A blood sample from all randomized/enrolled subjects will be collected prior to Day 1 dosing.
- q Biomarker plasma and serum collection (10 mL) should be sufficient for determination of ApoB48, lathosterol, lanosterol, desmosterol, among other biomarkers of interest.

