4.3 Baseline Lipids

For enrollment in Part B subjects are required to have screening triglyceride (TG) levels between 150 and 499 mg/dL, inclusive, and screening low-density lipoprotein cholesterol (LDL-c) levels between 100 and 200 mg/dL, inclusive. These lipids levels are allowed for enrollment in Part A but they are not required. During the Part B screening visit, fasting measurements of TG, total cholesterol (TC), and high-density lipoprotein cholesterol (HDL-c) will be obtained from plasma samples. LDL-c and non-HDL-c will then be derived as follows:

$$\text{LDL-c} = \text{TC} - (\text{TG}/5 + \text{HDL-c}), \text{ and}$$

$$\text{non-HDL-c} = \text{TC} - \text{LDL-c}.$$

Descriptive statistics for these five lipid parameters for subjects enrolled in Part B will be provided for each of the treatment groups and overall.

5 Concomitant Medications

Concomitant medications will be defined as medications, other than simvastatin and atorvastatin, taken on or after the date of first dose of randomly assigned study treatment (LY or placebo). This includes all medications initially taken prior to the date of first dose of randomly assigned study medication but with a stop date that is either missing or after the date of first dose of randomly assigned study medication. Those medications where the stop date is documented as prior to the date of first dose of randomly assigned study medication will be classified as prior medications. The prior medications will not be included in any summary reports.

The number (percent) of subjects who receive each concomitant medication, based on the WHODD preferred drug name, will be tabulated for Part B, but it is not planned to summarize in table format the concomitant medication usage for Part A of the study. However, by-subject listings of all concomitant medications that includes WHODD preferred drug name will be prepared separately for Parts A and B.

6 Pharmacodynamics Analyses

Pharmacodynamics (PD) analyses for this study will be based on fasting and post-prandial lipid profiles, fasting free fatty acids (FFA), β -hydroxybutyrate, apolipoprotein (Apo) B100, ApoC3,

proprotein convertase subtilisin/kexin type 9 (PCSK9), lipoprotein (a) [Lp(a)] and insulin, and body weight. All of these assessments will be collected longitudinally during the study.

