6.1 Fasting Lipid Profile Analyses

6.1.1 Fasting Lipid Profile Analyses in Part A

A fasting lipid profile will be collected from all subjects in each dosing period in Part A, except for dosing period 4 for Cohort 2 which prescribes dosing subjects in a fed state. Fasting measurements of TG, TC, and HDL-c will be obtained and fasting measurements of LDL-c and non-HDL-c will be derived from plasma samples collected just prior to dosing on the day of dosing, then at 24, 48 and 96 hours after dosing.

A last observation measurement will be derived for each subject using the last post-dose measurement of a lipid parameter. Change from baseline for each of the lipid parameters will be derived for each of the post-dosing time points (Day 1 [24 hours], Day 2 [48 hours], and Day 4 [96 hours]) and the last observation using the pre-dose measurement from the day of dosing as the baseline.

Descriptive statistics for the measurement at baseline and the measurement and change from baseline at each post-dose time point plus the last observation will be tabulated.

A mixed-effect repeated measures (MMRM) analyses will be conducted for each lipid parameter using the change from baseline values from Days 1, 2, and 4. The MMRM model for change from baseline will contain fixed effects for treatment, time, and their interaction, a random effect for subject, and the baseline measurement as a covariate. The covariance structure among the repeated measurements for a subject will be assumed to be common across subjects and modeled using an unstructured 3x3 matrix. Satterthwaite's approximation will be used to estimate denominator degrees of freedom. Any missing assessments will be assumed to be missing at random, so estimates of treatment effects from the model will be assumed to be unbiased. These analyses will be performed using the SAS procedure PROC MIXED. The tabular output for these MMRM analyses will present the least squares means, standard errors and 95% confidence intervals and Type 3 p-values for each main effect marginal. Pairwise contrasts of the least squares means between the LY dose levels and placebo along with the associated 95% confidence interval and Type 3 p-values will also be provided at each time point using LSMESTIMATE statements.

Plots of the least squares mean \pm standard error estimates for each lipid parameter over time (pre-dose through Day 4 post-dose) will be provided by treatment group.

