6.1.2 Fasting Lipid Profile Analyses in Part B

Fasting lipid profiles will be collected from all subjects in Part B just prior to dosing on the day of dosing, Day 7, Day 14, Day 21, and Day 28, and 7 (Day 35) days after stopping dosing of the randomized treatment. An additional follow-up assessment will be collected 14 (Day42) or 28 (Day 56) days after stopping dosing of the randomized treatment for Cohort 3 (5mg QD) and Cohorts 4 through 6, respectively.

A last on-treatment observation measurement will be derived for each subject using the last post-dose measurement for a lipid parameter taken while the subject is taking study medication during the 28-day treatment period. Change from baseline for each of the lipid parameters will be derived for each of the post-dosing time points (Days 7, 14, 21, 28, 35, and 42 or 56) and the last on-treatment observation using the pre-dose measurement from the first day of dosing as the baseline.

Descriptive statistics for the measurement at baseline and the measurement and change from baseline at each post-baseline time point plus the last observation will be tabulated.

An MMRM analysis will be conducted for each lipid parameter using the change from baseline values from Days 7, 14, 21, 28, 35, and 42. The MMRM model for change from baseline will contain fixed effects for treatment, time, and their interaction, a random effect for subject, and the baseline measurement as a covariate. Since the time points are evenly spaced the covariance structure among the repeated measurements for a subject will be assumed to be common across subjects and modeled using a autoregressive(1) 7x7 matrix. Satterthwaite's approximation will be used to estimate denominator degrees of freedom. Any missing assessments will be assumed to be missing at random, so estimates of treatment effects from the model will be unbiased.

These analyses will be performed using the SAS procedure PROC MIXED. The tabular output for these MMRM analyses will present the least squares means, standard errors and 95% confidence intervals and Type 3 p-values for each main effect marginal. Pairwise contrasts of the least squares means between the LY dose levels and placebo along with the associated 95% confidence interval and Type 3 p-values will also be provided at each time point using LSMESTIMATE statements.

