6.2.2 Post-prandial Lipid Profile Analyses in Part B

Measurement of the lipids TC, TG, HDL-c, LDL-c, and non-HDL-c will be obtained just prior to the midday meal on Days -1 and 28 of dosing. Post-meal measurements will be collected on both days at 0.5, 1, 2, and 4 hours after the meal for all subjects in Part B.

Change from baseline for each of the lipid parameters will be derived for each of the post-meal time points using the pre-meal measurement as the baseline, and the level of excursion within the 4-hour post-meal period will be determined using the post-meal AUC, as described in Section 6.2.1.

Descriptive statistics for the post-meal AUC at Days -1 and 28 as well as the difference between Days -1 and 28 will be presented by treatment group.

An ANCOVA will be conducted for each lipid parameter using the difference in post-meal AUC values from Day -1 to Day 28. The ANCOVA model will have a fixed effect for treatment, a random effect for subject, and the Day -1 post-meal AUC as a covariate.

Boxplots of the lipid values at pre-meal and each planned post-meal time point (0.5, 1, 2, and 4 hours post-meal) will be presented for each treatment group for both Day -1 and Day 28.

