6.3 Exploratory Biomarkers

The exploratory biomarkers FFA, β -hydroxybutyrate, and ApoB100 will be assessed from samples collected from all subjects in Part B on Day -1, Day 7, Day 14, Day 21, and Day 28,

plus 7 (Day 35) and 14 (Day 42) or 28 (Day 56) days after stopping dosing of the randomized treatment, while the biomarkers ApoC3, PCSK9, Lp(a) and insulin will only be collected on Day -1, Day 14, Day 28, Day 35, and Day 42 or 56. While the subjects are receiving randomized study medication samples will be collected just prior to dosing.

For each parameter a last on-treatment observation measurement will be derived for each subject using the last post-dose measurement for a parameter taken while the subject is taking study medication during the 28-day treatment period. Change from baseline for each parameter will be derived for each of the post-dosing time points (Days 7, 14, 21, 28, 35, and 42 or 56) and the last on-treatment observation using the Day -1 measurement as the baseline.

Descriptive statistics for the measurement at baseline and the measurement and change from baseline at each post-baseline time point plus the last observation will be tabulated.

An MMRM analysis will be conducted for each parameter using the change from baseline values. The MMRM model for change from baseline will contain fixed effects for treatment, time, and their interaction, a random effect for subject, and the baseline measurement as a covariate. Since the time points are evenly spaced the covariance structure among the repeated measurements for a subject will be assumed to be common across subjects and modeled using an autoregressive matrix. The analyses will be conducted and tabulated as described in Section 6.1.2.

Plots of the least squares mean \pm standard error estimates for each parameter over time (baseline through Day 56) will be provided by treatment group.

A last on-treatment observation analysis will be performed for change from baseline using an ANCOVA model with a fixed effect for treatment, a random effect for subject and the baseline value as a covariate. The analyses will be conducted and tabulated as described in Section 6.1.2.

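### The protocol assigns ultracentrifuge LDL-c to Part B PD analysis, but the SAP gives it no analysis and defines only a calculated LDL-c that depends on triglycerides

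*SAP*

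**What the plan says.** The protocol plans two LDL-c measures in Part B. One is calculated from TC, TG and HDL-c (10.6 and footnote l of the Part B schedule). The other is the ultracentrifuge value: 10.6 says lipid lowering will be quantified from the calculated panel "and by LDL-c ultracentrifugation methods in Part B only", and footnote o says "Low-density lipoprotein cholesterol for PD analysis will be evaluated by ultracentrifuge". Footnote o is attached to the schedule row that holds fasting LDL-c, FFA, β-hydroxybutyrate and ApoB100. That row is marked on Day -1, Days 7, 14, 21 and 28, and at follow-up.

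The SAP treats LDL-c as follows:

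- **4.3 (baseline).** "During the Part B screening visit, fasting measurements of TG, total cholesterol (TC), and high-density lipoprotein cholesterol (HDL-c) will be obtained", after which "LDL-c and non-HDL-c will then be derived as follows": LDL-c = TC - (TG/5 + HDL-c) and non-HDL-c = TC - LDL-c.
- **6.1.1 (Part A, fasting).** "fasting measurements of LDL-c and non-HDL-c will be derived from plasma samples".
- **6.1.2 (Part B, fasting).** "An MMRM analysis will be conducted for each lipid parameter using the change from baseline values". No LDL-c method is named, and baseline is the pre-dose value on the first dosing day.
- **6.2.2 (Part B, post-prandial).** "Measurement of the lipids TC, TG, HDL-c, LDL-c, and non-HDL-c will be obtained just prior to the midday meal on Days -1 and 28", with further samples after the meal.
- **6.3 (biomarkers).** FFA, β-hydroxybutyrate "and ApoB100 will be assessed from samples collected from all subjects in Part B on Day -1" and later days. LDL-c, which shares their schedule row, is not listed.

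**The concern.** The effect on fasting lipids is a secondary objective (Protocol 5.2, SAP 1.2.2), and the study rationale includes lowering both LDL-c and TG (Protocol 4.1). The measurement the protocol assigns to PD analysis has no planned analysis in this SAP. An analyst following the SAP would find one LDL-c definition and would use it.

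That definition subtracts one fifth of TG. Protocol 11.3.3 makes TG the marker of target engagement, and Part B enrols subjects with TG of 150 to 499 mg/dL. If TG falls on drug and not on placebo, any error in the one-fifth assumption enters the drug-placebo contrast for LDL-c, and the placebo group does not remove it.

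The choice between measures is also left open. Two LDL-c variables will exist in Part B, and the SAP does not say which answers the objective. Protocol 11.3.3 meanwhile allows the most sensitive PD analysis to be selected.

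**Working it through.** The plan states no power, effect size or SD for LDL-c, so there is no figure to reproduce. The check is algebra on the SAP's formula.

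**Inputs from the documents**

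- Calculated LDL-c = TC - (TG/5 + HDL-c) (SAP 4.3).
- TG at entry to Part B: 150 to 499 mg/dL (Protocol 7.1).

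**Assumptions, not in the documents**

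- TC = LDL-c + HDL-c + cholesterol in TG-rich particles.
- The ultracentrifuge value is free of the TG/5 term.
- TG-rich particles carry cholesterol and TG in the ratio 1:r, so their cholesterol is TG/r.
- The sizes of TG fall used below.

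**Step 1: dependence on TG.** At fixed TC and HDL-c, a 1 mg/dL fall in TG raises calculated LDL-c by 1/5 = 0.2 mg/dL. Over the entry range the subtracted term runs from 150/5 = 30.0 to 499/5 = 99.8 mg/dL.

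**Step 2: error at one visit.** Calculated minus true LDL-c = TG/r - TG/5 = TG × (1/r - 1/5).

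**Step 3: error in change from baseline, ratio fixed.** Error = (change in TG) × (1/r - 1/5). For TG falling from 400 to 250 mg/dL, the change is -150:

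- r = 4: -150 × (0.250 - 0.200) = -7.5 mg/dL
- r = 5: -150 × 0 = 0
- r = 6: -150 × (0.1667 - 0.200) = +5.0 mg/dL
- r = 8: -150 × (0.125 - 0.200) = +11.25 mg/dL

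A positive value means that an LDL-c reduction is understated; a negative value means it is overstated.

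**Step 4: wider range.** Write k = 1/r and take k from 0.12 to 0.25. The extremes come at TG 499 with a 50% fall (change -249.5): -249.5 × (0.12 - 0.20) = +20.0 and -249.5 × (0.25 - 0.20) = -12.5 mg/dL. At TG 250 with a 30% fall (change -75) the same k values give +6.0 and -3.75 (about -3.7) mg/dL.

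**Step 5: ratio shifts on treatment.** With TG falling from 250 to 175, the error is (k1 × 175 - k0 × 250) + 15.

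- k from 0.15 to 0.20: 35 - 37.5 + 15 = +12.5 mg/dL
- k from 0.20 to 0.17: 29.75 - 50 + 15 = -5.25 mg/dL

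**Step 6: non-HDL-c as written in SAP 4.3.** TC - LDL-c = TC - TC + TG/5 + HDL-c = TG/5 + HDL-c. The SAP abbreviation list defines non-HDL-c as TC minus HDL-c. With illustrative values TC 230, TG 250 and HDL-c 42, LDL-c is 230 - (50 + 42) = 138. The 4.3 formula then gives 230 - 138 = 92, and the abbreviation list gives 230 - 42 = 188 mg/dL.

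**The case against.** **The use of calculated LDL-c in the Part B model is inferred.** The formula is tied to the screening visit, and 6.1.2 does not repeat the word derived that 6.1.1 uses for Part A. LDL-c could be absent from 6.3 because it is handled as a lipid under 6.1.2. SAP 1.1 also refers the reader to the protocol for procedures and to the eCRF for variables. This stands. A reader might conclude that the SAP has chosen calculated LDL-c over the ultracentrifuge value, but the text does not say so. It leaves the source unstated while supplying only one definition, and that still needs repair if ultracentrifuge was intended.

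**Calculated LDL-c is planned in the protocol.** This also stands. Protocol 10.6 and footnote l plan it in Part B, and 10.6 includes the post-prandial period. A reader might infer that using it departs from the protocol, or that it should be removed from the post-prandial analyses. Neither follows. The gap is the missing analysis of the other measure.

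**Much of the error cancels.** At TG 499 and a ratio of 1:7, the single-visit error is 499 × (1/7 - 1/5) = -28.5 mg/dL, and a reader might take that as the bias. The SAP analyses change from baseline against placebo, so the part of the error common to both visits drops out. Likewise, 6.2.2 compares Day 28 with Day -1 AUC, so a stable meal artefact drops out. Only the change terms in Steps 3 to 5 matter.

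**The stakes are limited.** Safety is the primary objective, the study is not powered on hypothesis tests, and ApoB100, which does not involve TG/5, has its own model in 6.3. This lowers the severity but does not answer the point.

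SAP sections 9 and 10 defer PK/PD, PK/biomarker and additional non-PK DDI analyses to separate plans that are not available here. None is described as covering the fasting-lipid objective.

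**Conclusion.** The point holds as an unassigned measurement. The protocol designates ultracentrifuge LDL-c for Part B PD analysis, and the SAP neither mentions it nor says which LDL-c answers the fasting-lipid objective. On the natural reading of the SAP, the calculated value would be used.

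The algebraic link to TG is certain. Bias is not: it requires a true ratio other than 1:5, or a ratio that treatment changes. For the assumed fall from 400 to 250 mg/dL with a fixed ratio, the artefact runs from -7.5 (1:4) through 0 (1:5) to about +11 mg/dL (1:8). The documents give neither the ratio nor the expected TG fall, so a reader should not infer that the LDL-c result will be wrong, or in which direction.

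This should be fixed before database lock. It does not threaten the primary objective.

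**What to change.** - **SAP 6.1.2.** Name ultracentrifuge LDL-c as the Part B fasting LDL-c endpoint and apply the existing MMRM and last on-treatment ANCOVA. Use Day -1 as its baseline, because the schedule shows no ultracentrifuge sample on Day 1, and use Days 7, 14, 21, 28 and scheduled follow-up. Protocol 10.6.1 lists only Day -1, Day 28 and follow-up for fasting LDL-c, so note that the schedule's days are being followed.
- **Calculated LDL-c.** Keep it as a supportive fasting analysis in Part B. Keep it in the post-prandial analyses, which are exploratory, and label it there as TG-dependent.
- **SAP 4.3.** Correct non-HDL-c to TC - HDL-c, in line with the SAP's abbreviation list.

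The cost is SAP wording, one additional input variable with its own baseline day, and one corrected derivation. The samples and the assay are already in the protocol, so no subjects, visits or blood draws are added.

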- e Single 12-lead ECGs to be collected during Screening, triplicate ECGs (spaced approximately 1 minute apart) to be collected at all other time points. Subjects must be supine for at least 5 minutes prior to ECG collection. When ECG collections are scheduled at the same time point as any other tests, ECGs, followed by vital signs, must be recorded prior to any clinical laboratory, PK, PD, or biomarker blood sampling.
- f Collection to occur prior to dosing.
- g Vital signs to be measured include respiratory rate (Screening only), blood pressure, pulse rate, and temperature. Orthostatic blood pressure and pulse rate to be measured at all specified time points.
- h Refer to [Appendix 3](#) for the serum chemistry, hematology, and urinalysis clinical laboratory tests.
- i Serum pregnancy tests to be performed on female subjects only; serum FSH tests to be performed on postmenopausal female subjects only.
- j Serum TC, TG, and HDL-c will be measured; HDL-c will be used to calculate LDL-c and non-HDL-c.
- k Any leftover plasma will be stored for residual or LY3202328 metabolite assessment, after all study related needs are met.
- l Samples for serum chemistry will be obtained following a fast of at least 12 hours when a fasting lipid assessment is being performed at the same time. In case of dropouts or rechecks, subjects may not have fasted for 8 hours or 12 hours, as applicable, before the serum chemistry sample is taken.
- m Sample collection to occur just prior to meal.
- n LY3202328/placebo dosing will occur in the fasted state in all periods except the food effect period. Subjects being assessed for food effects on exposure will be given a high-fat/high-calorie meal prior to dosing during the food effect arm in Period 4.
- o A blood sample from all randomized/enrolled subjects will be collected prior to Day 1 dosing.
- p Biomarker plasma and serum collection (10 mL) should be sufficient for determination of ApoB48, lathosterol, lanosterol, desmosterol, among other biomarkers of interest.
- q Subjects will be discharged following Hour 24 procedures (i.e., Day 2).
- r A high-fat/high-calorie meal (containing approximately 60% fat, 20% carbohydrate, and 20% protein) will be given to subjects to 4 hours postdose for the post-prandial lipid assessment in all periods except for subjects in the food effect arm of Period 4.
- s Assessments can be performed any time predose

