| ANOVA | analysis of variance |
| ApoB | apolipoprotein |
| AST | alanine aminotransferase |
| AUC | area under the curve |
| BMI | body mass index |
| bpm | beats per minute |
| CI | confidence interval |
| Cmax | maximum concentration |
| CRP | clinical research physician |
| CRU | clinical research unit |
| CSR | clinical study report |
| DDI | drug-drug interaction |
| DGAT2 | Diacylglycerol acyltransferase 2 |
| ECG | Electrocardiogram |
| eCRF | electronic case report form |
| FFA | free fatty acid |
| HDL-c | high-density lipoprotein cholesterol |
| LDL-c | low-density lipoprotein cholesterol |
| Lp(a) | lipoprotein (a) |
| LY | LY3202328 |
| MAD | multiple ascending dose |
| MedDRA™ | Medical Dictionary for Regulatory Activities |
| mmHg | millimeters of mercury |
| MMRM | Mixed-effects model repeated measures |
| non-HDL-c | total cholesterol – high-density lipoprotein cholesterol |
| PCSK9 | proprotein convertase subtilisin/kexin type 9 |

| Abbreviation | Definition |
|------------------|---|
| PD | pharmacodynamic |
| PK | pharmacokinetic |
| PT | preferred term |
| QD | quaque die (once a day) |
| QT _{cf} | Fridericia corrected QT interval |
| SAD | single ascending dose |
| SAE | serious adverse event |
| SAP | Statistical analysis plan |
| SDTM | Study Data Tabulation Model |
| SOC | system organ class |
| TEAE | treatment emergent adverse event |
| TC | total cholesterol |
| TG | triglycerides |
| WHODD | World Health Organization Drug Dictionary |

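### SAP 4.3 derives non-HDL-c as TC − LDL-c, against the SAP's own definition of TC − HDL-c; programmed as written, the Part B baseline non-HDL-c summary is wrong

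*SAP*

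**What the plan says.** SAP 4.3 says that TC, TG and HDL-c are measured at the Part B screening visit and that "LDL-c and non-HDL-c will then be derived as follows". Two equations follow. The first is LDL-c = TC − (TG/5 + HDL-c). The second, as typeset, is "non-HDL-c} = \text{TC} - \text{LDL-c", that is, non-HDL-c = TC − LDL-c. The section then plans an output that uses both: "Descriptive statistics for these five lipid parameters for subjects enrolled in Part B", by treatment group and overall.

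The SAP's abbreviation list defines non-HDL-c as "total cholesterol – high-density lipoprotein cholesterol".

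The protocol prints no formula. Section 10.6 says HDL-c is measured "to calculate LDL-c and non-HDL-c". Footnote j of the Part A schedule (Appendix 2) reads "Serum TC, TG, and HDL-c will be measured; HDL-c will be used to calculate LDL-c and non-HDL-c", and footnote l of the Part B schedule has the same instruction. These statements fit the abbreviation list, but they do not spell out a formula that contradicts SAP 4.3.

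SAP 6.1.1 says that "fasting measurements of LDL-c and non-HDL-c will be derived from plasma samples" and gives no equation. SAP 6.2.1 and 6.2.2 also analyse non-HDL-c without one, and 6.1.2 refers to the lipid parameters without listing them.

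**The concern.** The SAP holds two incompatible definitions of one variable, and the wrong one is the working derivation rule. Non-HDL-c should be what remains of total cholesterol once HDL-c is removed. The 4.3 formula removes LDL-c instead.

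The direct consequence is a wrong non-HDL-c row in the Part B baseline table, in every treatment group and overall.

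There is also an indirect risk. SAP 4.3 contains the only LDL-c equation in either document. A programmer who needs calculated LDL-c for section 6 is likely to go there, and finds the wrong non-HDL-c line next to it. Part B fasting lipids are a secondary objective and post-prandial lipids an exploratory one. If the 4.3 formula were carried into those analyses, a fall in LDL-c would contribute nothing to the change in non-HDL-c, and a rise in HDL-c would count as an increase. Protocol section 4 expects the drug to lower LDL-c, so the error would hide part of the effect under study.

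**Working it through.** There is no stated figure to reproduce; the check is algebra followed by the entry ranges.

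**Inputs from the documents**
- LDL-c = TC − (TG/5 + HDL-c) (SAP 4.3).
- Non-HDL-c as printed = TC − LDL-c (SAP 4.3).
- Non-HDL-c as defined = TC − HDL-c (SAP abbreviation list).
- Part B entry: TG 150 to 499 mg/dL and LDL-c 100 to 200 mg/dL (SAP 4.3; Protocol 7.1).

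**Assumed:** HDL-c of 30 to 60 mg/dL, with 20 to 80 as a wider range. The documents give no HDL-c values.

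**Step 1. Substitute the LDL-c equation.**
- Printed: TC − [TC − (TG/5 + HDL-c)] = HDL-c + TG/5.
- Defined: TC = LDL-c + TG/5 + HDL-c, so TC − HDL-c = LDL-c + TG/5.
- Defined minus printed = LDL-c − HDL-c.

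The two agree only when LDL-c equals HDL-c. Since LDL-c is at least 100 at entry, the printed value is too low whenever HDL-c is below 100.

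**Step 2. Correct range, with no HDL-c assumption.**
- Lowest: 100 + 150/5 = 130 mg/dL.
- Highest: 200 + 499/5 = 299.8 mg/dL.

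The correct value always exceeds the subject's own LDL-c, by TG/5 = 30 to 99.8.

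**Step 3. Printed range and shortfall (mg/dL).**

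| HDL-c assumed | Printed formula | Too low by |
|---|---|---|
| 30 to 60 | 30 + 30 = 60 to 60 + 99.8 = 159.8 | 100 − 60 = 40 to 200 − 30 = 170 |
| 20 to 80 | 20 + 30 = 50 to 80 + 99.8 = 179.8 | 100 − 80 = 20 to 200 − 20 = 180 |

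**Step 4. Two worked profiles.**
- TG 150, LDL-c 100, HDL-c 50: TC = 100 + 30 + 50 = 180. Printed: 180 − 100 = 80. Defined: 180 − 50 = 130. The printed non-HDL-c is below the subject's LDL-c, which the definition does not allow.
- Midpoints of the entry ranges, LDL-c 150 and TG 324.5 (TG/5 = 64.9): defined 214.9. Printed 94.9 at HDL-c 30 and 124.9 at HDL-c 60. The shortfall is 120 (120/214.9 = 56%) or 90 (90/214.9 = 42%). The midpoints are an illustration; the plan does not say they are typical.

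**Step 5. Change from baseline, only if the formula is reused.** The TG/5 term is the same in both versions, so printed change − correct change = (HDL-c change) − (LDL-c change). Each 1 mg/dL fall in LDL-c counts 0 instead of −1, and each 1 mg/dL rise in HDL-c counts +1 instead of 0.

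**The case against.** This is probably a typing slip, with LDL-c written for HDL-c. The abbreviation list and the variable's name show the intent. SAP section 2 requires independent programming, independent review of outputs and a senior statistical review, and a table in which non-HDL-c falls below LDL-c would be noticeable. That lowers the risk but does not remove it: the final review includes consistency with the plan, and two programmers who both follow 4.3 would agree on the same wrong value.

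The documented effect is small, and this point stands. One row of a descriptive table is affected. Eligibility uses TG and LDL-c, not non-HDL-c. The 6.1.2 analysis takes its baseline from the pre-dose sample on the first dosing day, not from screening. The other four lipids in the table are unaffected, so mean non-HDL-c could be recovered from mean TC and mean HDL-c in the same subjects, although its SD, median and extremes could not.

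Reuse in section 6 can also be disputed. The 4.3 derivation is written for the Part B screening visit, and section 6 does not refer to it. In Part B, LDL-c for pharmacodynamic analysis is also measured by ultracentrifuge (Protocol 10.6; Part B schedule footnote o), so the fasting LDL-c analysis there need not use the 4.3 equation. The documents do not say whether the laboratory or the programmer calculates non-HDL-c. Reuse is therefore a possibility only, and the conclusion does not depend on it.

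The lower bound of 130 takes screening TG as at least 150. Protocol 7.4 lets a first value of 140 to 150 be averaged with a repeat, so a single-sample value could be slightly lower (100 + 140/5 = 128). This changes nothing of substance.

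**Conclusion.** The concern holds. SAP 4.3 and the SAP abbreviation list contradict each other, and the 4.3 formula is the wrong one. Followed as written, it makes the Part B baseline non-HDL-c summary wrong in every treatment group. The direction and form of the error (LDL-c − HDL-c) follow from the SAP's own equations alone; the size in mg/dL rests on the HDL-c values assumed above. The primary safety objective and the sample size are untouched. It should be corrected before the derivations are programmed, because the error is certain if the text is followed and the secondary fasting-lipid analyses have no non-HDL-c formula of their own.

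**What to change.** In SAP 4.3, replace the second equation with non-HDL-c = TC − HDL-c, matching the abbreviation list. Add a sentence saying that this derivation applies wherever non-HDL-c is analysed: 4.3, 6.1.1, 6.1.2, 6.2.1 and 6.2.2. The same derivation should serve the Part B interim lipid review in Protocol 11.3.4, which names non-HDL-c. The cost is a line or two of SAP text and one line of derivation code, with no new samples or analyses.
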